## **11. ETHICAL CONSIDERATIONS**

### **11.1 Regulation statement**

The study will be conducted according to the principles of the Declaration of Helsinki (59th WMA General Assembly, Seoul, Korea, October 2008) and in accordance with the Medical Research Involving Human Subjects Act (WMO).

### **11.2 Recruitment and consent**

This study will include 693 patients during a 48-month period. Annually, there are around 23,000 hospital admissions for AECOPD in the Netherlands (28). Nine centers will participate in the study: Amphia hospital (Breda), Erasmus MC (Rotterdam) Groene Hart (Gouda), Isala clinics (Zwolle), North West Hospital Group (Alkmaar), OLVG Oost (Amsterdam), the Sint Franciscus Gasthuis (Rotterdam), Zuyderland (Heerlen), Bravis Hospital (Bergen op Zoom/Roosendaal), MST (Enschede) and Catharina hospital (Eindhoven).

---

Informed consent forms will be presented before start of the study. Only patients that signed the informed consent will be entered in the study. Subject's written informed consent will be obtained prior to any study-related procedures. At any time patients have the right to withdraw from the study without any consequences for their ongoing treatment. For further details, see 8.4.

### **11.3 Objection by minors or incapacitated subjects (if applicable)**

**N/A**

### **11.4 Benefits and risks assessment, group relatedness**

**Benefits:** The main problem is the worldwide overuse of antibiotics contributing to the induction of global antibiotic resistance. We expect that a biomarker-based intervention using PCT to guide antibiotic treatment next to being non-inferior regarding treatment failure, will decrease the number of adverse effects and improve quality of life.

**Risks assessments:** Common side effects of antibiotics are diarrhoea and other gastro-intestinal complaints.

### **11.5 Compensation for injury**

The sponsor/investigator has a liability insurance which is in accordance with article 7, subsection 6 of the WMO. The sponsor (also) has an insurance which is in accordance with the legal requirements in the Netherlands (Article 7 WMO and the Measure regarding Compulsory Insurance for Clinical Research in Humans of 23th June 2003). This insurance provides cover for damage to research subjects through injury or death caused by the study.

### **11.6 Incentives (if applicable)**

**N.A.**

## **12. ADMINISTRATIVE ASPECTS, MONITORING AND PUBLICATION**

### **12.1 Handling and storage of data and documents**

Data will be handled and collected in compliance with ICH-GCP (Good Clinical Practice) and in accordance with prevailing national and international regulations, principles and guidelines such as VSNU code, NFU, WGBO and WMO and Erasmus MC policy on clinical trials ("Richtlijn wetenschappelijke integriteit Erasmus MC", "Erasmus MC Onderzoeksbeleid")

#### **Database**

For randomization, clinical data collection and central data management, Castor® will be used. Castor® is a web-based software tool designed to capture clinical study data. Castor® is hosted by an external party (Castor EDC), which is validated for conducting clinical trials in the Erasmus MC and meets all requirements to be ICH-GCP compliant.

The standard way to capture data in clinical studies is via e-CRFs which are specifically designed to collect study data in a structured format. Castor® allows sponsors (or their delegates) to design, manage and complete study specific e-CRFs. The e-CRFs can be completed for all participating subjects and can be reached from various locations in the world, allowing Castor® to be used for multicenter studies.

---

### **CRF design**

The sponsor of the study will design CRFs that accurately represent the protocol of the clinical study. The study specific CRFs will be designed in such a way that they accurately capture the required data for addressing the study objectives as outlined in the protocol of the clinical study. They should be parsimoniously (i.e. only collect what is needed to know, not what is nice to know) while at the same time being complete (i.e. no critical omissions leading to incomplete data).

### **Audit trail and data back-up**

One of Castor®'s prime features is that it keeps an audit trail, i.e. provides documentary evidence of the sequence of activities by user that have affected at any time a specific operation, procedure, or event. Data cannot be permanently deleted, ensuring proper backing-up of data. With regard to data entry, each change after submission will need to be accompanied by a reason for change.

### **Data entry**

Data entry will be done according to Standard Operating Procedures. Besides, study specific data entry guidelines will be provided to local datamanagers, promoting a uniform and standardized way of data entry and providing ways of working in case of exceptions (i.e. missings, unknowns etc). The local datamanagers will be trained in using the eCRF system Castor® prior to data entry start. All trainings will be documented conform GCP requirements.

## **12.2 Monitoring and Quality Assurance**

A study specific monitoring plan, compliant with NFU guidelines and the Erasmus MC requirements for the METC approved monitoring risk (i.e. minimal, medium or high, will be written. This study specific monitoring plan will focus both on quality assurance and cost efficiency.

Throughout the trial, a trained, qualified and independent monitor will periodically visit each participating site in order to, among other things, randomly check compliance with the protocol, compliance with in- and exclusion criteria, proper implementation and conduct of Informed Consent procedures, Source Data Verification (i.e. cross-check data in Castor® with patient dossier and vice versa) and SAE reporting.

Findings will be discussed with the Local Investigator and reported in a standard monitor report that will be shared with and filed by the Sponsor. The monitor will also feed any relevant findings back to the person(s) responsible for data validation (central data management).

### **Data validation/ Central Data management**

For critical data, i.e. data prone to errors, front-end validation checks (i.e. error messages) may be applied, preventing users from incorrect or illogical data entry.

Advanced back-end data consistency checks, focusing on missings, inconsistencies and outliers will be applied as batch cleanings to filter affected records. Affected records (i.e. missings, outliers) will be dealt with appropriately. That is, data queries will be generated and sent to the respective participating site. The participating site will have to address these queries until they are resolved satisfactory.

Timely data entry will be monitored throughout and reminders will be sent in case of delays.

---

A comprehensive study specific data management, detailing which data should be handled when, how, and by whom until they are deemed validated for data analyses, will be written prior to study commencement and reviewed/edited throughout the trial if so needed.

### **12.3 Amendments**

A 'substantial amendment' is defined as an amendment to the terms of the METC application, or to the protocol or any other supporting documentation, that is likely to affect to a significant degree:

- the safety or physical or mental integrity of the subjects of the trial;
- the scientific value of the trial;
- the conduct or management of the trial; or
- the quality or safety of any intervention used in the trial.

All substantial amendments will be notified to the METC and to the competent authority.

Non-substantial amendments will not be notified to the accredited METC and the competent authority, but will be recorded and filed by the sponsor.

*< Examples of non-substantial amendments are typing errors and administrative changes like changes in names, telephone numbers and other contact details of involved persons mentioned in the submitted study documentation.>*

### **12.4 Annual progress report**

The sponsor/investigator will submit a summary of the progress of the trial to the accredited METC once a year. Information will be provided on the date of inclusion of the first subject, numbers of subjects included and numbers of subjects that have completed the trial, serious adverse events/serious adverse reactions, other problems, and amendments.

### **12.5 End of study report**

The sponsor will notify the accredited METC and the competent authority of the end of the study within a period of 180 days. The end of the study is defined as the last patient's last visit.

In case the study is ended prematurely, the sponsor will notify the accredited METC and the competent authority within 15 days, including the reasons for the premature termination.

Within one year after the end of the study, the investigator/sponsor will submit a final study report with the results of the study, including any publications/abstracts of the study, to the accredited METC and the Competent Authority.

### **12.6 Public disclosure and publication policy**

This study is an investigator-initiated study. Therefore, arrangements concerning the public disclosure and publication between the sponsor and the investigator are not applicable. Results of this study will be disclosed to the public without any restrictions.

---

## **13. STRUCTURED RISK ANALYSIS**

### **13.1 Potential issues of concern**

Patients in both groups will either receive amoxicillin-clavulanic acid 875/125mg three times a day during five days or no antibiotic therapy. Common expected adverse events are: diarrhoea and other gastro-intestinal complaints. Patients will receive diary cards, these diary cards will be reviewed at each visits for symptoms, adverse events and exacerbations. In case of an adverse event measures will be taken to treat the existing adverse event.

### **13.2 Synthesis**

It is standard of care in all guidelines to administer prednisolone and antibiotics in the majority of COPD patients. Our drugs and dosing are within registration label and adhere to the Dutch guideline for treatment of COPD exacerbations in the hospital (15) (in line with GOLD 2018). We expect that risks of experiencing adverse events are acceptable for the subjects participating in the study.

---

4.1 Preface

Chronic obstructive pulmonary disease (COPD) is a prevalent disease, worldwide, and in the Netherlands with approximately 600.000 patients. COPD is currently the 4th leading cause of death worldwide and it is estimated to be the 3rd leading cause in 2020 [1–3]. It is also a leading cause of disability-adjusted life years. COPD accounts for just over 3% of the total health care budget in the European Union. The majority of these costs are attributed to acute exacerbations of COPD (AECOPD) [4]. Pulmonary physicians are well aware of overuse of both antibiotics and of prednisolone, but lack the tools to decide which medication to give on in the clinical setting. This overuse is important not only for the costs incurred for giving useless therapy, but there are also major side effects, the more frequent ones being gastrointestinal complaints. Finally, the overuse of antibiotics results in induction of antibiotic resistance, a worldwide grave concern. Biomarkers may aid towards a more personalized treatment of AECOPD by identifying which patient would benefit from antibiotics. Procalcitonin levels are minimally raised in viral infections, making it a relative specific diagnostic tool for bacterial infections [5]. Several trials have shown a reduction in antibiotic consumption in AECOPD when using a PCT-guided treatment algorithm [6–9]. PCT has not been tested in a clinical setting in a treatment algorithm specifically in COPD with the primary outcome measure being treatment failure

4.2 Scope of the analyses

The primary objective of this study is to show that at hospitalization for a severe exacerbation of COPD, PCT-guided treatment regarding antibiotic use is non-inferior to usual care consisting of prednisolone and or antibiotics, in terms of treatment failure at day 30 for patients hospitalized because of an acute exacerbation of COPD (AECOPD). Treatment failure is defined as an incomplete resolution of the clinical signs and symptoms associated with the AECOPD at day 30 after inclusion of the study (i.e. not reaching the baseline condition prior to the AECOPD).

5 Study Objectives and Endpoints

5.1 Study Objectives

We hypothesize that at hospitalization for a severe acute exacerbation for COPD, biomarker-guided treatment based on procalcitonin level to guide antibiotic administration is non-inferior to usual care consisting of prednisolone and or antibiotics, which is based on a clinical decision, in terms of treatment failure at day 30.

The secondary objectives are to establish that a biomarker-guided decision algorithm results in an improvement in quality of life, a decrease in consumption of antibiotics, and a reduction of important side effects.

5.2 Endpoints

The primary objective of this study is to show that at hospitalization for a severe exacerbation of COPD, PCT-guided treatment regarding antibiotic use is non-inferior to usual care consisting of prednisolone and or antibiotics, in terms of treatment failure at day 30 for patients hospitalized because of an acute exacerbation of COPD (AECOPD). Treatment failure is defined as disease-related mortality, endotracheal intubation, vasopressors, renal failure, lung abscess/empyema, pneumonia development or hospital readmission within 30 days after inclusion of the study.

The secondary objectives of this study are to assess the following secondary endpoints:

- Treatment failure defined as an incomplete resolution of the clinical signs and symptoms associated with the AECOPD at day 30 after inclusion of the study (i.e not reaching the baseline condition prior to the AECOPD) scored using the modified Anthonisen criteria.
- Change in Quality of Life on day 1, 10, and after 30 days using the COPD Assessment Test (CAT)
- EXACT – Respiratory symptoms scale (at admission, at day 10 and at day 30 after admission)
- Time to complete resolution of symptoms according to daily symptom diaries evaluating the modified Anthonisen criteria
- Start of antibiotic therapy after an initial opposite decision (after 48 hours)
- Non-Invasive ventilation after 72 hours of admission
- Length of hospitalization
- Re-exacerbation within 30 days
- Side effects (gastro-intestinal complaints, allergic reactions)
- Cumulative antibiotic consumption
- Cumulative prednisolone consumption

6 Study Methods

6.1 General Study Design and Plan

- Study design: prospective, randomized-controlled trial. Patients will be randomized to biomarker-guided treatment (based on blood procalcitonin level) or to usual care. In the usual care arm, and in the biomarker guided-arm in case of high ($> 0.25\mu\text{g/L}$) procalcitonin, patients will receive amoxicillin-clavulanic acid.
- Type of Comparison: non-inferiority.
- Type of control(s): usual care
- Level and method of blinding (e.g. double-blind): The patient and the outcome assessor will be blinded for the allocated treatment strategy. Two independent physicians will be selected per center to be the outcome assessors. The patient will not be blinded for the treatment itself (prednisolone with or without antibiotic therapy).
- Method of treatment assignment: We will use a block-randomisation with randomly alternating blocks of 4 and 6 patients (random permuted block randomisation). The randomisation will be stratified per center.
- At what point in time subjects are randomized relative to treatments, events and study periods: Upon presentation at the emergency department, patients will be clinically

judged for in- and exclusion criteria, among which indication for hospitalization. When eligible the patient will be notified about the study. When the patient is interested in participating, the patient information form will be discussed by the treating physician. The participation being voluntarily and the opportunity to discontinue participation will be made clear by the treating physician. Informed consent will be requested with at least two hours of time to decide

- Sequence and duration of all study periods: screening will occur on the first day of admission as described above, baseline characteristics will be collected within 24 hours of admission, active treatment will be 5 days, follow-up will be 30 days.

6.2 Inclusion-Exclusion Criteria and General Study Population

Inclusion criteria

- COPD, according to GOLD 2018 definition [10]
- Indication for hospitalization because of acute severe exacerbation of COPD, as defined by GOLD 2018 and modified Anthonisen criteria [10–12]
- Presence of at least 2 major symptoms of the modified Anthonisen criteria (acute deterioration in sputum volume, sputum purulence and dyspnea) or the presence of 1 major symptom and 1 minor symptom (coughing, wheeze, nasal discharge, sore throat, fever) [11]
- Post-bronchodilator FEV1/FVC < 0,70 and FEV1% < 80%pred. within last 5 years
- At least 40 years
- Smokers or ex-smokers with > 10 packyears
- Written informed consent
- Start of symptoms no more than 5 days before admission

Exclusion criteria

- Indication for ICU and or non-invasive ventilation < 72h of admission
- Pneumonia (radiologically confirmed)
- Sepsis
- Current asthma, or COPD before age 40.
- Clinically relevant heart failure or myocardial ischemia
- Chronic use of immunosuppressants, including prednisolone
- Known bronchiectasis as a primary diagnosis (bronchopathy is not an exclusion criterium)
- Colonisation with *Pseudomonas* spp. or other micro-organisms in recent cultures (last 60 days) not susceptible to amoxicillin-clavulanic acid
- Pregnancy
- Recent exacerbation (last 28 days)
- Pre-treatment with antibiotics (by general practitioner) during the 5 days prior to admission. Use of maintenance therapy with antibiotics, such as azithromycin is not considered an exclusion criterium.

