**8.2 Randomisation, blinding and treatment allocation**

Upon presentation at the emergency department, patients will be clinically judged for in- and exclusion criteria, among which indication for hospitalization. When eligible the patient will be notified about the study. When the patient is interested in participating, the patient information form will be discussed by the treating physician. The participation being voluntarily and the opportunity to discontinue participation will be made clear by the treating physician. Informed consent will be requested with at least two hours of time to decide. Randomisation will occur by a computer-based program. We will use a block-randomisation with randomly alternating blocks of 4 or 6 patients (random permuted block randomisation) and with stratification by center and with stratification by pre-treatment with antibiotics. The patient will not be blinded for the treatment received (prednisolone with or without antibiotic therapy) but the patient will be blinded for the treatment strategy (usual care or PCT-guided treatment). The participating centers will appoint two physicians that will be outcome assessors. The outcome assessors will be blinded for the treatment strategy.

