### **10. STATISTICAL ANALYSIS**

There will be two analysis populations for this study:

1. The Intention-to-Treat (ITT) population is defined as all randomised patients who took at least one dose of study drug.
2. The Per-Protocol (PP) population is defined as a subset of ITT population constituted by those patients who: a) met all inclusion/exclusion criteria, b) attained a sufficient compliance to the treatment received, treatment with prednisolone and/or antibiotics, when prescribed on admission for at least 5 days, and c) did not present serious deviations from the protocol.

The analysis of all the efficacy variables will be performed on both the ITT and the PP populations in order to assess the robustness of the findings from the ITT population. All the demographic and baseline patients' characteristics and safety outcomes will be analysed using the ITT population.

All efficacy variables will be analysed for ITT and the PPS, and the PP population will be considered the primary population for assessing efficacy.

---

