6.3 Randomization and Blinding

Upon presentation at the emergency department, patients will be clinically judged for in- and exclusion criteria, among which indication for hospitalization. When eligible the patient will be notified about the study. When the patient is interested in participating, the patient information form will be discussed by the treating physician. The participation being voluntarily and the opportunity to discontinue participation will be made clear by the treating physician. Informed consent will be requested with at least two hours of time to decide. Randomisation will occur by a computer-based program. We will use a block-randomisation with randomly alternating blocks of 4 and 6 patients and with stratification by center. The outcome assessors at day 30 will be blinded for the treatment arm. Two independent physicians will be selected per center to be the outcome assessors. The patient will also be blinded for the treatment strategy (usual care or PCT-guided), but not for the received treatment (antibiotics or no antibiotics next to prednisolone).

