8.2.2 Per Protocol Population

- All subjects who:
 - met all inclusion/exclusion criteria,
 - attained a sufficient compliance to the treatment received, treatment with prednisolone and/or antibiotics, when prescribed on admission for at least 5 days,
 - did not present serious deviations from the protocol.

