8.2.3 Safety Population

- All subjects who received any study treatment (including control) but excluding subjects who drop out prior to receiving any treatment.

The analysis of all the efficacy variables will be performed on both the ITT and the PP populations in order to assess the robustness of the findings from the ITT population.

All the demographic and baseline patients' characteristics and safety outcomes will be analysed using the ITT population.

All efficacy variables will be analysed for ITT and the PPS, and the PP population will be considered the primary population for assessing efficacy.

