8.3 Covariates and Subgroups

(ICH E3; 9.7.1, 11.4.2.1. ICH E9; 5.7)

As mentioned above, patients will be randomized. This will remove the effect of possible confounders.

The randomization and treatment allocation will be stratified by center. We will use alternating blocks of 4 and 6 patients which will lead to a maximum imbalance of 3 participants per center. We consider this to be an acceptable amount of imbalance.

At this moment we do not have the intention to analyze subgroups. We do not exclude the possibility of exploratory subgroup analysis but these results can only be presented as summary statistics.

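### SAP 6.2 carries a different eligibility list from the protocol, so the primary per-protocol set is not uniquely defined; the SAP also leaves out a randomisation stratum

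*SAP*

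**What the plan says.** **Eligibility.** SAP 6.2 has its own inclusion and exclusion list. It excludes "Pre-treatment with antibiotics (by general practitioner) during the 5 days prior to admission", exempting only maintenance antibiotics. It also differs from protocol 4.2/4.3 on symptom onset, asthma, chronic prednisolone and infection at another site.

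**Primary population.** SAP 8.2.2 requires per-protocol patients to have "met all inclusion/exclusion criteria". Protocol section 10 sets the same condition: "a) met all inclusion/exclusion criteria, b) attained a sufficient compliance to the treatment received". Neither definition points to a section or a protocol version. SAP 8.2.3 states that "the PP population will be considered the primary population for assessing efficacy", and protocol section 10 agrees.

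**Stratification.** Protocol 8.2 randomises "with stratification by center and with stratification by pre-treatment with antibiotics". SAP 6.1 says "The randomisation will be stratified per center", and SAP 6.3 describes "alternating blocks of 4 and 6 patients and with stratification by center". SAP 8.3 also gives centre only and derives a bound from it: "which will lead to a maximum imbalance of 3 participants per center". The primary model in SAP 9 has a random centre effect and a fixed treatment effect, with no term for pre-treatment.

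**The concern.** In a confirmatory non-inferiority trial, membership of the primary set must be fixed before outcomes are seen. Here the same phrase gives two different sets, depending on which document's list the analyst opens.

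Under the SAP list, some patients whom the protocol admits and randomises would leave the per-protocol set but stay in the intention-to-treat set. This would include patients in the pre-treatment stratum who had GP antibiotics in the 5 days before admission. Three things follow:

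- power is lost;
- the result applies to a narrower population than the one enrolled;
- the two populations differ for reasons unrelated to adherence, which weakens the robustness comparison planned between them.

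If the list is chosen after the data are seen, the primary result also loses credibility.

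**Working it through.** **1. The two lists side by side**

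| Criterion | Protocol 4.2/4.3 | SAP 6.2 |
|---|---|---|
| Symptom onset before admission | up to 7 days | up to 5 days |
| GP antibiotics in the 5 days before admission | not an exclusion; pre-treatment is a stratum (8.2) | excluded |
| Current asthma together with COPD | admitted | excluded |
| Chronic prednisolone | prednisone equivalent up to 10 mg admitted | excluded, no dose allowance |
| Infection at another site | excluded | not listed (sepsis only) |
| Pack-years | 10 or more | more than 10 |

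The first four rows make the SAP stricter and the fifth makes it looser. The pack-year row may be a lost underline in the text extraction, and nothing below depends on it.

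**2. Reproducing the plan's sample size**

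Inputs from protocol 4.4 and 10.4: failure 20.4% (usual care) and 16.7% (PCT-guided), margin 5 points, 80% power, one-sided alpha 0.025, or 0.0492/2 = 0.0246 after the interim look.

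- Variance sum: 0.204 × 0.796 + 0.167 × 0.833 = 0.1624 + 0.1391 = 0.3015.
- Distance from the margin: 0.05 + (0.204 − 0.167) = 0.087.
- n per arm = (z_alpha + 0.8416)² × 0.3015 / 0.087².
- Alpha 0.025 (z = 1.960) gives 312.6, so 313. Alpha 0.0246 (z = 1.967) gives 314.2, so 315.

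Both match the plan. The total of 693 is 630 × 1.10. A full 10% dropout leaves 693 × 0.90 = 623.7, or 79.7% power, so no reserve remains for further exclusions.

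**3. Power if the SAP list is applied**

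Power = Φ(0.087/SE − 1.967), with SE = √[0.3015/(N/2)]. The documents give no share of affected patients, so the shares below are assumptions. The planned rates are assumed to hold in the reduced set.

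| Share removed from 630 | N | SE | Power |
|---|---|---|---|
| 0% | 630 | 0.0309 | 80.1% |
| 10% | 567 | 0.0326 | 75.8% |
| 30% | 441 | 0.0370 | 65.0% |
| 40% | 378 | 0.0399 | 58.4% |

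Solving for N without assuming a share: power is 75% at N = 555.8, so it falls below 75% once 75 patients (12%) are removed. It is 70% at N = 494.4, so it falls below 70% once 136 (22%) are removed.

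**4. Leaving out the pre-treatment stratum**

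Assumptions: 315 per arm, pre-treated share 20%, 30% or 40%, usual-care failure 30% in pre-treated patients against 17%, 15.5% or 14% in the others, the same relative risk (0.167/0.204) in each stratum, centre ignored. The stratified SE of the risk difference is 0.8%, 1.3% or 1.7% smaller than the unstratified SE. An interval that ignores the stratum is therefore slightly too wide:

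- one-sided type I error is 0.0237, 0.0232 or 0.0227 against a nominal 0.0246;
- power is 80.2%, 80.3% or 80.5% unstratified, against 80.6%, 81.0% or 81.4% stratified.

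On the log odds-ratio scale, which the SAP uses, adjustment widens the interval by 0.8–1.7%, so there is no precision gain to claim on that scale.

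**5. Imbalance bound**

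A block of 6 can leave at most 3 more patients on one arm within a stratum. With two strata per centre the bound is 3 + 3 = 6. Simulated permuted blocks of 4 and 6 gave the same maxima: 3 in one stratum, 6 over two.

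**The case against.** Within the protocol, the per-protocol definition can only refer to the protocol's own sections 4.2 and 4.3, so the doubt lies on the SAP side alone. SAP 15 lists the study protocol among the documents to be used, and it cites version 8 with version 9 pending. The simplest explanation is a restatement that fell behind an amendment. In that case a sensible analyst would use the protocol list and lose nobody, and patients enrolled under stricter earlier criteria would be unaffected in any event. The disputed criteria are fixed before randomisation, so applying either list does not by itself bias the comparison between arms. Intention-to-treat results are also reported, so any divergence would be visible. The removal shares are assumed, and the stratum effect is small and conservative.

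Most of this stands as a limit on size. Version lag remains an inference, and it would explain the conflict without resolving it: the SAP nowhere says that the protocol criteria govern, or which version applies to which patient. Comparing the confidence-interval half-width with the 5-point margin would also be uninformative, because the intact design already has 6.1 points. The argument here rests on power instead.

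**Conclusion.** The concern holds and should be fixed. The textual conflict is certain: followed as written, the SAP gives a different primary set from the protocol, an incomplete account of the randomisation and an imbalance bound of 3 where 6 is correct.

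The numerical effect is conditional. It is zero if the protocol list is used. If the SAP list is used, power falls to between 75.8% and 58.4% for assumed losses of 10% to 40%, with planning rates unchanged. Omitting the stratum costs 0.4 to 0.9 points of power under the stated assumptions and does not inflate type I error on the risk-difference scale.

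A related leftover belongs in the same revision: SAP 4.2 and the rationale in SAP 9.3 still treat symptom non-resolution as the primary endpoint, whereas SAP 5.2, 9 and 9.2 use the composite.

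**What to change.** Revise the SAP before database lock:

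1. Reconcile 6.2 with protocol 4.2/4.3. This review takes no position on which clinical criterion is right.
2. State in 8.2.2 that per-protocol eligibility is judged by the protocol criteria in force when each patient was enrolled.
3. Name centre and antibiotic pre-treatment as stratification factors in 6.1, 6.3 and 8.3, and change the imbalance bound to 6 per centre.
4. Account for pre-treatment as a stratum in the protocol's risk-difference estimate, or by standardising from the model, without claiming a narrower odds-ratio interval.
5. Align 4.2 and the 9.3 rationale with the composite endpoint, keeping symptom non-resolution as key secondary.

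The cost is a text revision. Pre-treatment is already recorded because randomisation uses it, and the evaluable target stays at 315 per arm.
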